3.1.3 Designation of Study Eye

Study eye will be defined as the eye that meets all of the inclusion and none of the exclusion criteria. If both eyes meet criteria, the eye with higher pterygium vascularity grading will be chosen as the study eye. If both eyes have the same pterygium vascularity grading, the right eye (OD) will be determined as the study eye.

[figure not shown]
3.2 Randomization and Masking

Stage 1 is open-label. Subjects in Stage 1 who discontinue before enrollment is complete may be replaced in the study. Replacement subjects will be assigned unique subject numbers.

Stage 2 is double-masked. Approximately 75 subjects with pterygium will be randomly assigned to receive 1 of 3 treatments [REDACTED] in a 1:1:1 ratio. Randomization schedule will be optimized to achieve a balanced distribution of treatment assignment by stratifying randomization by baseline pterygium hyperemia grading [REDACTED]. [REDACTED] Subjects and study personnel, including but not limited to investigators, study staff,

central lab, clinical monitors, and designated staff within the Sponsor and the Sponsor's representatives, will remain masked to the study treatment assignments. There will be a small dedicated unmasked team comprised of Sponsor and Sponsor representatives that will manage IP supply, IRT services, and randomization schematics.

Figure 1. Study Flowchart

Upon DMC Review of Stage 1 Safety Data and Determination MTD, the study will move on to Stage 2.

[figure not shown]

Table 1. Schedule of Visits and Procedure for RMP-A03-001: Stage 1

Procedures	Screening Day -60 to -1 (Visit 1)	Baseline Day 1 (Visit 2)	Post-dose Day 1 (Visit 3)	Follow-up/Exit ¹ Day 7+1 day (Visit 4)
Informed Consent	X			
Inclusion/Exclusion	X	X		
Demographics	X			
Medical/Ophthalmic History	X	X		X
Concomitant Medications	X	X		X
Physical examination	X	X	X	X
Vital Signs	X	X	X	X
Urine Pregnancy Test ²	X	X		X
Clinical Labs	X			X
Adverse Events ³		X	X	X
Ocular Comfort Index	X	X	X	X
BCDVA	X	X	X	X
Intraocular Pressure	X	X	X	X
Slit Lamp Biomicroscopy	X	X	X	X
Indirect Ophthalmoscopy	X	X	X	X
Eyedrop Instillation Evaluation	X			
Study Drug Administration		X ⁴		
Study Drug Dispensing			X	
Study Drug Collected				X ⁵

¹ Every effort should be made to complete all Exit procedures at Early Termination

² A negative result on a urine pregnancy test before administration of study drug for women of childbearing potential is required for eligibility

³ AEs should be assessed before and after administration of study drug

⁴ First dose to be administered by in the clinic by study staff after completion of all Baseline assessments

⁵ Collect kit dispensed at Exit visit

Table 2: Schedule of Visits and Procedure for RMP-A03-001: Stage 2

Procedures	Screening Day-60 to -1 (Visit 1)	Baseline Day1 (Visit 2)	Follow-up Day 7±1 day (Visit 3)	Follow-up Day 14±3 days Phone call ¹ (Visit 4)	Follow-up Day 28±3 days (Visit 5)	Follow-up Day 56±4 days (Visit 6)	Follow-up/ Exit ² Day 84±5 days (Visit 7)
Informed Consent	X						
Inclusion/Exclusion	X	X					
Demographics	X						
Medical/Ophthalmic History	X	X	X	X	X	X	X
Concomitant Medications	X	X	X	X	X	X	X
Vital Signs	X	X	X		X	X	X
Urine Pregnancy Test ³	X	X					X
Clinical Labs	X						X
Adverse Events ⁴		X	X	X	X	X	X
Ocular Comfort Index	X	X	X		X	X	X
BCDVA	X	X	X		X	X	X
Intraocular Pressure	X	X	X		X	X	X
Pterygium Photography	X	Study Eye	Study Eye		Study Eye	Study Eye	Study Eye
Pterygium Assessments	X	Study Eye	Study Eye		Study Eye	Study Eye	Study Eye
Slit Lamp Biomicroscopy	X	X	X		X	X	X
Indirect Ophthalmoscopy	X	X	X		X	X	X
Eyedrop Instillation Evaluation	X						
Study Drug Administration		X ⁵					
Study Drug Dispensing		X					
Study Drug Collected							X ⁶

¹ Schedule the Telephone visit (Visit 4) on Day 14. Change in medical history or concomitant medications should be assessed by the investigator for AEs. Study drug compliance issues and reeducation of subjects should be documented in the source documents

² Every effort should be made to complete all Exit procedures at Early Termination

³ A negative result on a urine pregnancy test before administration of study drug for women of childbearing potential is required for eligibility

⁴ AEs should be assessed before and after administration of study drug

⁵ On Day 1, the first dose of the study drug will be administered in the clinic by study staff after completion of all Baseline assessments

⁶ Collect kit dispensed at Exit Visit

4 STUDY ENDPOINTS

4.1 Safety Endpoints in Stage 1 and Stage 2

- Rates of adverse events (AEs)

4.2 Efficacy Endpoints in Stage 2

4.2.1 Primary Efficacy Endpoint

- Change from baseline in pterygium hyperemia grading at Day 28

4.2.2 Secondary Efficacy Endpoints

- Change from baseline in pterygium characteristics at Day 28
 - length
 - encroachment onto the cornea
 - size at limbus

5 ANALYSIS SETS

5.1 Enrolled Analysis Set: Stage 1 and Stage 2

The Enrolled Analysis Set will include all enrolled subjects (non-screen failures). This analysis set will be used for all listings.

5.2 Safety Analysis Set: Stage 1 and Stage 2

The Safety Analysis Set will include all subjects who were randomized and took at least 1 dose of the study drug. Subjects in this analysis set will be analyzed as treated. In Stage 1, this analysis set will be used for all analyses. In Stage 2, this analysis set will be used for all safety analyses.

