#### 4.5.RANDOMIZATION

Randomization will be implemented in Stage 2. Consented subjects who meet all enrollment criteria will be randomly assigned to receive 1 of 3 treatments (RMP-A03 Dose 1, RMP-A03 Dose 2 or vehicle) in a 1:1:1 ratio. Randomization schedule will be optimized to achieve a balanced distribution of treatment assignment by baseline ██████████.

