## **9.2.ANALYSIS POPULATIONS/SETS**

For Stage 1 and Stage 2, the safety population/set will include all subjects who receive at least 1 dose of investigational product.

For Stage 2:

- Intent-to-Treat (ITT): The ITT set will include all randomized subjects.
- Modified Intent-to-Treat (mITT): The mITT set will include all randomized subjects who receive at least 1 dose of investigation product and have at least one post-dose primary efficacy assessment.
- Per Protocol (PP): The PP set will include subjects in the mITT who do not have significant protocol deviations that affect the primary endpoint analysis. Protocol deviations will be assessed prior to database lock and unmasking.

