3 STUDY OVERVIEW

3.1 Study Design

This is a first-in-human study with a 2-stage design. Only 1 eye per subject will be enrolled into the study.

See [Figure 1](#) for study flowchart, [Table 1](#) and [Table 2](#) for schedules of visits and procedure for Stage 1 and Stage 2 of RMP-A03-001, respectively.

3.1.1 Stage 1

Stage 1, is an open-label dose escalation, 7-day study to determine the maximum tolerated dose (MTD) of the 4 evaluated doses of RMP-A03 in healthy volunteers. Four escalating doses of RMP-A03 ocular suspension [REDACTED] will be evaluated in Stage 1, given that no safety concerns are identified with each escalating dose. Up to 5 subjects are planned for enrollment into each dose cohort. The first cohort will begin with the lowest dose of study drug (RMP-A03 ocular suspension [REDACTED]).

At the screening visit, following informed consent, demographic information, relevant medical and ophthalmic history will be recorded. All prescription and over-the-counter medications taken 30 days prior to the screening and during the study will be recorded (diagnostic eye drops do not need to be recorded). Urine pregnancy test must be performed for women of childbearing potential (WOCBP). Screening assessments will include a complete physical examination, heart rate and blood pressure, clinical labs, comprehensive ophthalmic assessments, pterygium assessments, and the ocular comfort questionnaire. At Day 1 baseline visit, after completing all

required assessments and confirming eligibility, the study subject will instill a single eye drop of RMP-A03 to the study eye one time at Day 1. The study staff will observe the eye drop instillation. Post-baseline evaluations on Day 1 will include physical examination, heart rate and blood pressure, comprehensive ophthalmic assessments, the ocular comfort questionnaire, and AE collection. Upon confirmation of acceptable tolerability and no immediate safety concerns, study drug will be dispensed at the end of Day 1 and subjects will be instructed to instill 1 drop of study medication in the study eye 3 times daily (TID, at least 3 hours apart), starting from the morning of Day 2 to Day 6. On Day 7, subjects will return to the clinic, and a single eye drop of RMP A03 will be administered in the study eye before completion of the final examinations (see Table 1-1 for study visits and procedures and Figure 1 for the study schematic).

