7.4 Safety Analyses

Safety and tolerability will be assessed throughout the study by examination of AEs, ophthalmic examinations, clinical laboratory tests, vital signs, and physical examinations (Stage 1). Safety related tables and listings will be based on the Safety Analysis Set.

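### SAP 5.2 makes randomization a condition of the Safety Analysis Set in both stages, so as written no subject from the non-randomized Stage 1 can enter it

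*SAP*

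**What the plan says.** The SAP section is headed "5.2 Safety Analysis Set: Stage 1 and Stage 2", so a single definition serves both stages. That definition reads "The Safety Analysis Set will include all subjects who were randomized and took at least 1 dose of the study drug". The same paragraph adds "In Stage 1, this analysis set will be used for all analyses", and SAP 7.4 states "Safety related tables and listings will be based on the Safety Analysis Set".

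Stage 1 has no random allocation. SAP 3.2 says "Stage 1 is open-label" and describes random assignment for Stage 2 alone. Protocol 4.5 says "Randomization will be implemented in Stage 2". Four dose cohorts are filled in sequence, with a safety review between them.

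The protocol defines the population differently. For both stages, Protocol 9.2 says that "the safety population/set will include all subjects who receive at least 1 dose of investigational product", and the synopsis repeats this. SAP 8, which lists departures from the protocol analysis, has one entry, on the baseline hyperemia covariate. It does not mention the safety set.

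**The concern.** Two conditions joined by a conjunction must both be met, and in Stage 1 the first can never be met. The rule therefore excludes every Stage 1 subject from the set that the SAP then prescribes for all Stage 1 analyses.

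Safety and tolerability in Stages 1 and 2 is the primary objective of this first-in-human study. If the rule is followed, the Stage 1 adverse event, ophthalmic and vital sign summaries have no subjects. If the programmer sets the rule aside, the population for the primary objective rests on an unwritten decision, and the report must explain why the analysis did not follow the SAP. The SAP definition is also narrower than the protocol's, and the narrowing is not declared.

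**Working it through.** **Inputs**

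| Item | Value | Source |
|---|---|---|
| SAP rule | randomized AND dosed | SAP 5.2 |
| Protocol rule | dosed | Protocol 9.2, synopsis |
| Stage 1 allocation | sequential cohorts, not randomized | SAP 3.1.1, 3.2; Protocol 4.1, 4.5 |
| Stage 1 size | 4 cohorts, up to 5 each | SAP 3.1.1, 9 |
| Stage 2 size | 3 arms, about 25 each | SAP 9 |

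**Step 1. Reproduce the planned counts.** Stage 1: 4 × 5 = 20, which matches the SAP's upper limit of 20. Stage 2: 3 × 25 = 75, which matches the SAP's figure.

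**Step 2. Apply each rule.** Assume that every planned subject is dosed and that every Stage 2 subject is randomized.

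| Rule | Stage 1 | Stage 2 |
|---|---|---|
| SAP 5.2 as written | 0 of 20 | 75 of 75 |
| Protocol 9.2 | 20 of 20 | 75 of 75 |

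The Stage 1 zero does not depend on the planned size. Fewer cohorts, or the replacements that SAP 3.2 allows, would change the denominator but not the zero.

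**Step 3. See whether another set fills the gap.** The ITT, mITT and PP sets are each labelled for Stage 2 only (SAP 5.3 to 5.5). The Enrolled Analysis Set covers Stage 1 without a randomization condition, but it is assigned to listings (SAP 5.1) and to the table that counts subjects per analysis set (SAP 6.1). No set other than the Safety Analysis Set is assigned to the Stage 1 safety summaries.

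**Step 4. Sort the Stage 1 outputs.**

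- *Empty as written:* summaries on the Safety Analysis Set, such as treatment-emergent adverse events (SAP 7.4.1), ophthalmic evaluations (7.4.2) and vital signs (7.4.4).
- *Not emptied:* the analysis-set count table in SAP 6.1, whose base is the Enrolled set. It would itself show zero in the Stage 1 safety row.
- *Undetermined:* safety listings. SAP 5.1 puts all listings on the Enrolled set, and SAP 7.4 puts safety listings on the Safety set. Laboratory results (7.4.3) and Stage 1 physical examinations (7.4.5) are planned as listings only, so whether they are filled depends on which section governs.

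**Step 5. Look for the same slip elsewhere.** SAP 6.8 defines concomitant medication relative to the first day on randomized study drug. Stage 1 subjects have no such day. The definition of prior medication in the same section refers simply to the first dose and works in both stages.

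**The case against.** The strongest reply is that nobody could mistake the intent. The heading names Stage 1, the paragraph assigns the set to Stage 1, the SAP says that it is based on a protocol that gives the right definition twice, and no rival Stage 1 population is plausible. A zero count would show at the first table run, so the slip would not quietly bias an estimate. Absence from SAP 8 fits a drafting slip better than a concealed change of method. All of this stands, and it limits the weight of the point. It does not make the rule correct: the population for the primary objective should be readable from the SAP, not inferred against its wording.

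A reader might infer three stronger things that the documents do not support.

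- *That every Stage 1 output is empty.* The Enrolled set still supports the SAP 6.1 table and, under SAP 5.1, the listings.
- *That dose-escalation decisions are compromised.* Under Protocol 4.1 and 4.2 the Safety Committee reviews the data of all subjects in the preceding cohort. That review does not use this analysis set.
- *That Stage 2 safety data would be lost for subjects dosed without a randomization record.* The documents report no such subject. The error described in SAP 7.3 concerns assignment under incorrect strata. Those subjects were still randomized and stay in the set.

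**Conclusion.** The point holds as a wrong rule with an obvious correction. Under the literal SAP wording, 0 of up to 20 dosed Stage 1 subjects enter the Safety Analysis Set, against up to 20 of 20 under Protocol 9.2. The affected outputs are the Stage 1 summaries based on that set. Stage 2 is the same under both rules, up to 75, provided that all planned subjects are randomized and dosed. The conclusion rests on Stage 1 having no random allocation, which both documents support, and on reading the two conditions in SAP 5.2 as jointly required. It should be corrected because it concerns the primary objective and contradicts the protocol without saying so. Nothing in the documents suggests that a safety decision or a treatment comparison would change.

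**What to change.** 1. In SAP 5.2, delete the three words that impose randomization, so that the set is everyone who received study drug at least once, as in Protocol 9.2. Keep the as-treated rule and spell it out: by dose cohort in Stage 1, by treatment received in Stage 2. With the protocol definition restored, SAP 8 needs no entry on this.
2. Reconcile SAP 5.1 with SAP 7.4 by stating once which set supports the safety listings.
3. In SAP 6.8, define concomitant and new concomitant medication relative to the first dose of study drug, so that the definitions also work in Stage 1.

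The cost is a few words in the SAP. No planned Stage 2 count changes, no extra data are needed, and there is no statistical downside.

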5.3 Intent-to-Treat (ITT): Stage 2 only

The ITT Analysis Set will include all subjects who were randomized. Subjects in this analysis set will be analyzed as randomized. This analysis set will be used for subject disposition, demographics and baseline characteristics, medical history, protocol deviations, and concomitant medications.

5.4 Modified Intent-to-Treat (mITT): Stage 2 only

The mITT Analysis Set will include all subjects who were randomized and took at least 1 dose of the study medication and have at least one post-dose primary efficacy assessment. Subjects in this analysis set will be analyzed as randomized. Efficacy analysis will be performed on this analysis set.

5.5 Per-Protocol (PP) Analysis Set: Stage 2 only

The PP Analysis Set will include subjects in the mITT Analysis Set who do not have significant protocol deviations that affect the primary endpoint analysis. Protocol deviations will be assessed and the PP Analysis Set selection will be documented in a memo prior to database lock and unmasking. Subjects in this analysis set will be analyzed as randomized. Efficacy analysis will be performed on this analysis set.

6 STUDY SUBJECTS

6.1 Analysis Sets

The number and percentage of subjects in each analysis set will be summarized by treatment group and overall, for the Enrolled Analysis Set. A listing of analysis sets will also be presented.

6.2 Subject Disposition

Subject disposition will be summarized by treatment group (including overall). The number of subjects who were enrolled, randomized, completed, or discontinued from the study, as well as the reason for discontinuation, will be summarized by treatment group. A listing of subject disposition will also be presented.

6.3 Demographic and Baseline Characteristics

Demographic and baseline characteristics will be summarized by treatment group (including overall), including age, sex, ethnicity, race, height, weight, and study eye. A listing of demographics and baseline characteristics will also be presented.

6.4 Medical History

Medical history will be coded using version 24.1 or later of the Medical Dictionary for Regulatory Activities (MedDRA).

Medical history will be summarized by treatment group (including overall), System Organ Class (SOC) and Preferred Term (PT). Multiple histories will be counted only once per subject in each summary level. A listing of medical history will also be presented.

6.5 Inclusion/Exclusion Criteria and Subject Eligibility

Subject eligibility, e.g., inclusion and exclusion criteria failures will be listed for all screened subjects.

6.6 Protocol Deviations

The number and percentage of subjects with any major protocol deviations will be summarized by treatment group (including overall) and deviation category. Multiple deviations will be counted only once per subject in each summary level. All protocol deviations will be presented in a listing.

6.7 Investigational Product Administration and Extent of Exposure

Duration of study drug exposure (days) will be summarized by treatment group (including overall). A listing of study drug exposure will also be presented. Duration of exposure to study drug is calculated as (date of last dose – date of first dose + 1).

6.8 Concomitant Medications

The World Health Organization Drug Dictionary (WHO-DD) will be used to categorize verbatim descriptions of non-study medications into the Anatomical Therapeutic Chemical (ATC) classification system. Each verbatim name will be classified by anatomical main group (ATC level 1), therapeutic subgroup (ATC level 2), pharmacological subgroup (ATC level 3), chemical subgroup (ATC level 4), and trade name.

Prior medication is defined as any medication with a stop date prior to the first dose of study drug. Prior medications will not be summarized but will be provided in a listing. Concomitant medications refer to non-study medications used on or after the first day of receiving the randomized study drug. Among concomitant medications, those started after the first day of receiving the randomized study drug will be defined as new concomitant medication and will be flagged.

Concomitant medications, and new concomitant medications if needed, will be summarized by treatment group (including overall), ATC classification (ATC level 3 and PT). All prior and concomitant medications will be presented in a listing.

7 STATISTICAL ANALYSIS METHODS

7.1 General Considerations

7.1.1 Statistical Notation and Presentation

For continuous variables the following descriptive statistics will be provided: number of subjects, mean, standard deviation (SD), standard error (SE), minimum, maximum, and median. For categorical variables, descriptive statistics will include the number and percentage of subjects in each category, using either the number of subjects in the treatment group or the number of subjects with non-missing values as the denominator for the percentages.

In general, minimum and maximum values will be rounded to the precision of the original value; means and medians will be rounded to one decimal place greater than the precision of the original value; and SDs and SEs will be rounded to two decimal places greater than the precision of the original value. Percentages for summarizing categorical data will be rounded to one decimal place. P-values will be presented with four decimal places and values less than 0.0001 will be presented as <0.0001 .

In the case where a safety laboratory variable is recorded as “ $> x$ ”, “ $\geq x$ ”, “ $< x$ ” or “ $\leq x$ ”, a value of x will be taken for summary. In listings, these data will be presented as recorded with the sign.

By subject listings, including data at scheduled and unscheduled visits, will be sorted by treatment group, subject, visit, and timepoint.

7.1.2 Baseline and Change from Baseline

Baseline is defined as the last non-missing observation obtained prior to the administration of the study drug. Change from baseline is defined as post-baseline result minus baseline result.

7.1.3 Study Day

Study day will be calculated as the number of days from first dose of study drug.

For events/assessments on or after first dose of study drug:

- Study day = date of event (or date of assessment) – date of first dose of study drug + 1.

For events/assessments before first dose of study drug:

- Study day = date of event (or date of assessment) – date of first dose of study drug.

7.1.4 Handling of Missing or Partial Dates

No missing data will be imputed for the safety analysis, except for missing or partial start dates of AEs with the imputation rule that missing component(s) will be assumed as the most

conservative value(s) possible. For example, AEs with missing start dates as treatment-emergent adverse events (TEAEs) will be conservatively captured as follows:

- If “day” is the only missing field, impute the “day” as the date of first dose of study drug if their “month” and “year” are the same; otherwise, the first day of the non-missing month.
- If “day” and “month” are the only missing fields, impute the “day” and “month” as the date of first dose of study drug if their “year” is the same; otherwise, January 1 of the non-missing year.

Non-study medications with missing or partial dates will be imputed similarly. If the start date is unknown and end date is “ongoing” then the non-study medication will be considered a concomitant medication, but not a new concomitant medication.

Date imputation will only be used for computational purposes, e.g., defining the treatment-emergent status. Actual data values as they appear in the original CRFs will be shown in data listings.

